## 10.4 STATISTICAL ANALYSES

### 10.4.1 General Approach

- Participants in phase I will be evaluated for safety, reporting the toxicities noted per dose level.
- Participants in phase II will have their response rate reported along with a confidence interval.

### 10.4.2 Analysis of the Primary Endpoints

- Participants enrolled in phase I will have the grades and types of toxicity reported at each dose level. The overall estimate of the fraction of participants who have a DLT at the RP2D will be reported.
- Participants evaluated in phase II will have the fraction with clinical responses reported, with a 95% confidence interval.

### 10.4.3 Analysis of the Secondary Endpoints

- The secondary objectives for phase I are to describe pharmacokinetic properties of KPT-8602 in MDS participants and to evaluate safety and tolerability of KPT-8602 in combination with Inqovi in MDS participants. The AUC, half-life, and Css of KPT-8602 will be evaluated in participants, by dose level using descriptive statistics.
- The secondary objectives for phase II are to evaluate the safety and tolerability of the agent as measured by the grades and types of toxicity noted for the agent at each dose level and reported descriptively.

### 10.4.4 Safety Analyses

The safety and tolerability of the agent will be evaluated by reporting the grades and types of toxicity noted for the agent at each dose level.

#### 10.4.4.1 Safety stopping rules

Phase I will follow a 3+3 dose-escalation design, paused for review when the toxicity reaches the criteria in Section [3.1.1](#).

For phase II, our goal toxicity rate is less than 20%.

Phase II toxicity assessment will use Bayesian toxicity monitoring with maximum probability of DLT of 0.2, prior distribution (1,1), maximum participants 43, minimum number of participants before stopping 9, cohort size 1, and posterior probability > 80%. Using this approach, the study would be paused for review for toxicities that meet the definition of DLT in 3/9, 4/11, 5/15, 6/20, 7/24, 8/28, and 9/32 participants.

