## Phase I/II Study Schema

### 3.1.1 Dose Limiting Toxicity (DLT)

The DLT evaluation window will be the first 28 days of study treatment. No dose reductions or interruptions are allowed during the DLT observation period.

A DLT is defined as any of the following treatment-related toxicities (based on CTCAE Version 5.0):

- Any Grade 5 toxicity, unless due to underlying disease, disease progression, or accidental injury.
- Any Grade  $\geq 3$  non-hematologic toxicity, except:
  - Grade 3 or 4 isolated electrolyte abnormalities that resolve, with or without intervention, to Grade  $\leq 2$  within 72 hours
  - Grade 3 nausea, vomiting, or diarrhea that does not require/prolong hospitalization, does not require TPN or NGT feeding, and resolves to Grade  $\leq 2$  within 72 hours
  - Grade 3 fatigue, fever, flu-like symptoms, or headache lasting  $\leq 72$  hours
  - Grade 3 laboratory abnormalities that are not associated with organ pathology
  - Direct complications of cytopenia(s) due to active myeloid malignancy, such as:
    - Grade 3 or 4 febrile neutropenia
    - Grade 3 or 4 infection
    - Grade 3 or 4 hypotension explained by sepsis
    - Grade 3 or 4 hemorrhage/bleeding
- Confirmed Hy's law cases, defined as:
  - AT (ALT or AST) elevation  $> 3$  times upper limit of normal (ULN), AND
  - Total bilirubin  $> 2$  times ULN, without initial findings of cholestasis (elevated serum alkaline phosphatase), AND

- No other immediately apparent possible causes of AT elevation and hyperbilirubinemia, including, but not limited to, viral hepatitis, pre-existing chronic or acute liver disease, or the administration of other drug(s) known to be hepatotoxic.
- In the absence of active MDS, hematologic DLTs for each arm include:
  - any Grade  $\geq 4$  decrease ANC or PLTs lasting more than 28 days.
- Any adverse reaction that leads to dose reduction or withdrawal of KPT-8602.

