## 10.2 STATISTICAL HYPOTHESIS AND SAMPLE SIZE DETERMINATION

The trial will begin with a phase I dose-escalation phase using a standard 3+3 design which will enroll participants with relapsed/refractory HR-MDS. Up to 18 participants may be enrolled based on the 3+3 design.

Participants will be eligible for the DLT evaluation if  $\geq 90\%$  (9 out of 10 doses) of KPT-8602 and  $\geq 80\%$  (4 out of 5 doses) of Inqovi were taken within the DLT period. Participants not evaluable for toxicity, will be replaced in the dose level.

Phase II will use a Simon's minimal two-stage design, applied separately as noted below:

- Trial will be conducted using a Simon minimax two-stage phase II trial design to rule out an unacceptably low response rate of 25% ( $p_0=0.25$ ) in favor of an improved response rate of 45% ( $p_1=0.45$ ) in order to determine if the combination of KPT-8602 with Inqovi will be able to improve upon an expected 30-40% response rate in participants who have received other agents. With two-sided alpha=0.05 and beta=0.20, the first stage will enroll 21 evaluable participants, and if 0 to 5 of the 21 have a response, then no further participants will be accrued. If 6 or more of the first 21 participants have a response, then accrual would continue until a total of 43 evaluable participants have been treated. If there are only 6-16 participants with a response out of 43 participants, this would be an uninterestingly low response rate. If there were 17 or more of 43 (39.5%) who experienced a response, treatment would be sufficiently interesting to warrant further study in later trials. The probability of early termination under the null (25%) response rate is 56.7%.

It is expected that up to 12-15 participants with MDS may be accrued per year. Thus, in order to accrue up to  $18 + 43 = 61$  participants (which may be reduced by up to 6 if up to 6 participants in phase I may be included in phase II), and to allow for a small number of inevaluable participants (12), it is expected that 3-4 years may be required to accrue the required 73 participants. Note: To allow for screen failures (7), the accrual ceiling will be set at 80 participants for the purposes of the NIH accrual ceiling.

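### The Phase II toxicity rule has no numeric trigger before nine participants, so it can delay a pause that a third DLT has already made certain

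*Combined protocol and SAP*

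**What the plan says.** Section 10.4.4.1 introduces the Phase II rule with "For phase II, our goal toxicity rate is less than 20" percent. The design parameters are "maximum probability of DLT of 0.2, prior distribution (1,1), maximum participants 43", followed by "minimum number of participants before stopping 9, cohort size 1, and posterior probability > 80" percent. The resulting rule is that the study is "paused for review for toxicities that meet the definition of DLT in 3/9, 4/11, 5/15, 6/20, 7/24, 8/28, and 9/32 participants". Crossing a boundary leads to a pause and a review, not to termination.

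Three other places bear on the size of the point:
- Section 3.1.1: "The DLT evaluation window will be the first 28 days of study treatment".
- Section 10.2, on accrual: "It is expected that up to 12-15 participants with MDS may be accrued per year".
- Section 10.2, on the total sample size: "which may be reduced by up to 6 if up to 6 participants in phase I may be included in phase II".

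Outside the Bayesian rule, Section 13.1 allows the study to be suspended at any time if the risk is judged unacceptable. Section 7.4.1 has the research team discuss each treated participant weekly. Neither gives a count or a rate that triggers action in Phase II.

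**The concern.** A cohort size of 1 means that the rule is evaluated after each participant, but the minimum of 9 keeps it silent until then. At 9 the boundary is three DLTs. If three have occurred among the first 3 to 8 participants, no later outcome can bring the count at 9 below three. The rule's answer is then known, but the rule as written does not act on it.

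At stake is the exposure of participants enrolled between the third DLT and the ninth participant. They would be treated after the plan's own criterion for a review has in substance been met, and their outcomes cannot alter whether that review takes place. Any earlier pause would rest on judgement, not on the prespecified rule.

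**Working it through.** **Inputs.** Limit 0.20, prior Beta(1,1), threshold 0.80, minimum 9, maximum 43, boundaries from 3/9 to 9/32 (Section 10.4.4.1); DLT window 28 days (Section 3.1.1); accrual 12 to 15 per year and up to 6 carried-over participants (Section 10.2). True DLT rates of 10% to 40% are assumed scenarios.

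**1. Reproduce the plan's boundaries.** With x DLTs in n participants, the posterior is Beta(1 + x, 1 + n − x), so P(rate > 0.2) = 1 − BetaCDF(0.2; 1 + x, 1 + n − x). At n = 9, x = 3 gives 0.879 and x = 2 gives 0.678, so the boundary is 3. The other boundaries give 0.927 (4/11), 0.918 (5/15), 0.892 (6/20), 0.891 (7/24), 0.892 (8/28) and 0.893 (9/32). All seven reproduce. Three DLTs also trigger at n = 10 (0.839) but not at n = 11 (0.795).

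**2. Posterior with three DLTs before participant 9.** The values are 0.998 (3/3), 0.993 (3/4), 0.983 (3/5), 0.967 (3/6), 0.944 (3/7) and 0.914 (3/8). All exceed both 0.80 and the 0.879 at 3/9.

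**3. How often this arises, starting from zero.** Let T be the participant with the third DLT, so that P(T = k) = C(k − 1, 2) p³ (1 − p)^(k − 3). The number of further participants before the pause is 9 − T, at most 9 − 3 = 6. For example, at p = 0.2, P(T ≤ 8) = 1 − (0.8⁸ + 8 × 0.2 × 0.8⁷ + 28 × 0.2² × 0.8⁶) = 1 − 0.797 = 0.203.

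| True DLT rate | P(T ≤ 8) | P(T = 3), the maximum of 6 | Mean further participants if T ≤ 8 | Mean saving over all trials |
|---|---|---|---|---|
| 10% | 3.8% | 0.1% | 2.4 | 0.09 |
| 20% | 20.3% | 0.8% | 2.7 | 0.54 |
| 30% | 44.8% | 2.7% | 3.0 | 1.33 |
| 40% | 68.5% | 6.4% | 3.3 | 2.28 |

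**4. Effect of pausing at the third DLT.** An exact forward recursion to n = 43 compares the plan's rule with the same rule plus a pause at a third DLT before participant 9.

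| True DLT rate | P(pause), plan | P(pause), changed | Expected participants before a pause or 43: plan → changed |
|---|---|---|---|
| 10% | 9.7% | 9.7% | 39.97 → 39.87 |
| 20% | 54.3% | 54.3% | 27.45 → 26.91 |
| 30% | 91.5% | 91.5% | 15.61 → 14.28 |
| 40% | 99.5% | 99.5% | 10.74 → 8.46 |

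The probabilities are equal by construction: every sequence that pauses early under the change would have paused at 9 anyway.

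**5. If Phase I participants count toward the nine.** Section 3.1.2 allows at most 1 DLT in 6 at the MTD. With six carried over, the earliest third DLT is participant 8 (one in Phase I, then participants 7 and 8), so the excess is at most 9 − 8 = 1. Given one DLT in the six, this has probability p²: 0.2² = 4% at a true rate of 20%, and 0.4² = 16% at 40%.

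**6. Time.** At 12 to 15 participants per year, one participant takes 12/15 = 0.8 to 12/12 = 1 month. The maximum of 6 takes 4.8 to 6 months.

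**The case against.** A minimum sample size is a deliberate parameter that limits early false alarms, and nothing in the section is miscalculated. That defence is sound against applying the 80% threshold from n = 3, which would raise the probability of a pause at a true rate of 20% from 54.3% to 69.8%. It does not apply to acting only when the existing pause is already certain, which leaves that probability at 54.3%.

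A reader might infer that the plan forbids a pause before nine, or obliges the site to keep enrolling. It does neither: Sections 13.1 and 7.4.1 leave room to stop on judgement. What is missing is a numeric trigger.

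A reader might also infer that the further participants have no effect on the decision. That is true only of whether the pause occurs. The boundary leads to a review, and their data could inform its outcome: the posterior is 0.993 at 3/4 but 0.879 at 3/9.

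Two objections on size stand. High true rates are less likely to reach Phase II: at most 1 DLT in 6 has probability 0.6⁶ + 6 × 0.4 × 0.6⁵ = 23% at a true rate of 40%. In addition, the 28-day DLT window is about as long as the interval between enrolments, so about one further participant may have started before a third DLT is recognised, whatever the rule says.

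**Conclusion.** The point holds as a gap in the rule, not as an error in its boundaries. Below nine participants there is no numeric Phase II trigger, and a third DLT by participant 8 already settles that the 3/9 boundary will be crossed, provided that no DLT is reclassified and no participant is removed from the count.

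The size is modest. Starting from zero, the mean saving from acting at once is about 0.1 to 2.3 participants at true DLT rates of 10% to 40%. Six is the extreme, reached only if the first three participants all have DLTs, and the delay of about 5 to 6 months belongs to that case alone. If six Phase I participants count, the maximum excess is 1. The maximum therefore ranges from 1 to 6, and the documents do not settle which applies. The change is still worth making because it does not alter the probability of a pause and matters most when the regimen is most toxic.

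**What to change.** In Section 10.4.4.1, state that the study is paused for review as soon as a third DLT is observed within the first 10 participants, so that the minimum of 9 does not delay a pause that is already certain. Keep the other boundaries. Ten is the right limit because three DLTs still trigger at n = 10 but not at n = 11 under the plan's own threshold.

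In the same section, state whether Phase I participants included in Phase II count in the toxicity monitoring.

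The cost is two sentences. No boundary from 9 onward changes. The one downside is that the review may have data on fewer than nine participants.

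### The Phase II toxicity pause list in 10.4.4.1 is cut short: the stated rule also gives 10/37 and 11/41, so no correct boundary is printed for participants 37 to 43

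*Combined protocol and SAP*

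**What the plan says.** Section 10.4.4.1 (Safety stopping rules) gives every input of the Phase II rule: "maximum probability of DLT of 0.2", a (1,1) prior, "maximum participants 43", "minimum number of participants before stopping 9", a cohort size of 1, and a posterior probability above 80%. As the output of that rule it lists pauses for review at "3/9, 4/11, 5/15, 6/20, 7/24, 8/28, and 9/32 participants". The list ends there.

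Section 10.2 confirms the planned size: if stage 1 succeeds, "accrual would continue until a total of 43 evaluable participants have been treated". Section 3.1.4 sends the reader to 10.4.4 for the safety stopping rules. No other section prints a boundary beyond 32 participants, says that monitoring ends at 32, or says what count applies between two listed sample sizes.

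**The concern.** The rule is stated for up to 43 participants, but the last printed trigger is at 32. The printed counts are what a study team will use from day to day; staff are unlikely to recompute a beta posterior after each participant. Late in stage 2 a team with only the list could do one of two things:

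- treat monitoring as finished, and so lose some chance of pausing when the DLT rate is too high; or
- carry the count of 9 forward, and so pause on evidence that does not meet the stated 80% criterion.

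The text does not say which was meant.

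**Working it through.** **Inputs (all from 10.4.4.1).** Limit 0.2; prior Beta(1,1); posterior threshold above 0.80; first look at n = 9; a look after every participant; maximum n = 43.

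**Formula.** With x DLTs in n participants the posterior for the DLT rate p is Beta(1 + x, 1 + n − x). The study pauses at n if P(p > 0.2 | x, n) > 0.80. For this prior the posterior probability equals P(Binomial(n + 1, 0.2) ≤ x), which gave the same values as a check. The boundary at n is the smallest x that satisfies the inequality.

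**Step 1: reproduce the printed list.** The first n at which each count becomes the boundary:

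| Boundary | Posterior | Posterior with one DLT fewer | Printed? |
|---|---|---|---|
| 3/9 | 0.879 | 0.678 | yes |
| 4/11 | 0.927 | 0.795 | yes |
| 5/15 | 0.918 | 0.798 | yes |
| 6/20 | 0.892 | 0.769 | yes |
| 7/24 | 0.891 | 0.780 | yes |
| 8/28 | 0.892 | 0.790 | yes |
| 9/32 | 0.893 | 0.79996 | yes |
| 10/37 | 0.878 | 0.784 | **no** |
| 11/41 | 0.882 | 0.795 | **no** |

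The seven printed pairs match exactly. This confirms the inputs and the listing convention (first n for each count). The 32-participant entry is right although 8/32 comes within rounding of 0.80, because it does not exceed it.

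**Step 2: how far each count reaches.** 9/36 gives 0.809 and 9/37 gives 0.784, so 9 is the boundary for n = 32 to 36 only. 10/40 gives 0.818 and 10/41 gives 0.795, so 10 covers 37 to 40. 11/43 gives 0.846 and 10/43 gives 0.746, so 11 covers 41 to 43. Exactly two entries are missing, and they affect 43 − 36 = 7 participants (7/43 = 16%).

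**Step 3: effect on the probability of a pause.** This is an exact recursion over n = 1 to 43. At each n the distribution of the DLT count is updated by one Bernoulli(p) participant, and the probability at or above the boundary is removed as a pause. The futility look at 21 is left out, so the figures suppose that accrual runs to 43 unless a toxicity pause occurs.

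| True DLT rate | Full rule to 43 | Monitoring lapses after 36 | List read as ending at 32 | 9 carried forward to 43 |
|---|---|---|---|---|
| 20% | 54.3% | 52.7% | 50.8% | 62.3% |
| 25% | 77.4% | 75.1% | 72.4% | 84.7% |
| 30% | 91.5% | 89.7% | 87.3% | 95.5% |
| 35% | 97.6% | 96.6% | 95.2% | 99.0% |

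With monitoring to 36, the loss is about 2 percentage points at 25% and 30% and about 1 point at 35%. Carrying 9 forward lets the study pause with a posterior of 78.4% at 9/37, falling to 61.7% at 9/43.

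**The case against.** The strongest reply is that nothing printed is wrong. The rule comes first and is complete; the list is introduced as its result, and anyone with the inputs can derive 10/37 and 11/41. This stands: the table is truncated, and the rule itself is neither missing nor contradicted.

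A reader might infer that participants 33 to 43, the last quarter of Phase II, have no boundary at all. The documents do not support that. A cohort size of 1 implies a check after every participant, so each count must hold until the next one, and the printed 9 is correct through 36. Reading the list as the end of monitoring at 32 also sits badly with the stated maximum of 43. The figures for that reading (72.4% and 87.3% at true rates of 25% and 30%) are a less natural worst case.

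Three further points limit the harm. Carrying 9 forward errs towards caution, and its consequence is a pause for review, not termination. The gap is reached only if at least 6 of the first 21 participants respond and stage 2 opens. The research team also meets weekly and the principal investigator reviews each participant's adverse events (7.4.1), and the study may be suspended for unacceptable risk (13.1). These safeguards reduce the practical risk but do not supply the missing numbers.

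**Conclusion.** The point holds as an incomplete list. The seven printed boundaries are correct; 10/37 and 11/41 are absent, and participants 37 to 43 have no correct printed trigger. The likely cost is about 2 percentage points of pause probability at true DLT rates of 25% to 30% if monitoring lapses after 36, or 4 to 5 points on the less natural reading that it ends at 32. Carrying 9 forward has the opposite effect: 8 points more pauses at a true rate of exactly 20% (62.3% against 54.3%), on posteriors below the stated threshold.

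The boundaries rest only on the inputs in 10.4.4.1. The pause probabilities also assume independent participants with a common DLT rate, a look after every participant from the ninth, and no stop for futility. The correction is worth making because these counts are the working safety triggers. It does not call the design into question.

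**What to change.** In 10.4.4.1, end the list with 9/32, 10/37 and 11/41, and add that each count applies until the next listed sample size: 3 at 9–10, 4 at 11–14, 5 at 15–19, 6 at 20–23, 7 at 24–27, 8 at 28–31, 9 at 32–36, 10 at 37–40 and 11 at 41–43. The cost is a line or two of text. The limit, prior, threshold, minimum and maximum all stay as they are; the change only prints what the stated rule already requires.

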#### 10.4.5 Baseline Descriptive Statistics

Standard sample statistics will be provided for each cohort and overall.

#### 10.4.6 Planned Interim Analyses

As indicated above in Section **10.2**, participants in phase II will be evaluated after 21 participants have been treated, an evaluation will be performed of the responses at that point to determine suitability to enroll the remaining participants. Specifically, the trial will proceed to the second stage if there are least 6 responses out of 21 participants with HR-MDS with a safety follow-up through day 28 required for the interim analysis, enrollment to the cohort will be halted to allow for an analysis by the study investigator. A brief memo will be created by the study investigator to document the number of responses in the first stage and will be reviewed by the PI and study team. The memo will be provided to study sponsor prior to continuation of accrual. Also, if the required number of responses is observed before that time, the memo will be generated, reviewed and provided to the study sponsor at that point without a pause in accrual. Response rates will be calculated using the revised International Working Group (IWG) 2006 response criteria for all responses, except hematologic improvement (HI) responses which will use the IWG 2018 response criteria, as described in the protocol.

#### 10.4.7 Sub-Group Analyses

Results from phase II will be presented according to MDS-subgroup, disease risk category and genomic features.

#### 10.4.8 Tabulation of individual Participant Data

None will be provided.

#### 10.4.9 Exploratory Analyses

All exploratory analyses will be performed with descriptive intent, largely done separately by cohort. In the cases in which a statistical test is performed, the tests will be done without formal adjustment for multiple comparisons, but in the context of the number of tests performed.

##### 10.4.9.1 Anslyses of Patient-Reported Outcomes

Evaluating Compliance and Feasibility of Administering PRO: Received PRO forms will be checked versus the timing schedule and considered as valid if they fall within the specified days of the scheduled assessment window. Compliance rates will be calculated as the number of received valid forms over the number of expected forms. Compliance rates will be described using summary statistics.

We will collectively refer to the symptom scales and functional well-being subscales from the EORTC QLQ C30, individual symptom items from the PRO-CTCAE items, PROMIS physical function T-scores, and the single item overall side effect bother as PRO outcomes. These PRO outcomes will be summarized by descriptive statistics, such as mean, percentages, frequency, standard deviation, and 95% confidence interval. The change in PRO outcomes over time will be evaluated using paired-t test or Wilcoxon signed rank test depending on the distributional assumptions. When appropriate, a linear or generalized linear mixed model will be used to make inferences on the trajectory of PRO outcomes. Error bar graphs for each of the PRO outcomes will be constructed at each time point. Because the PRO-CTCAE complements the CTCAE, we will use the same analysis approach for the PRO-CTCAE. The traditional method of reporting AEs

over the course of a clinical trial is by taking the maximum value. This single value is then reported descriptively. Because many participants enter clinical trials with symptoms at baseline, it is desirable to perform baseline adjustment in the analysis of symptomatic adverse events.[\(56\)](#) The baseline adjustment method consists of two steps. First, determine the maximum AE score for a participant over the study period post baseline. Second, if the maximum AE score is worse than baseline, then use the maximum AE score. However, if the maximum AE score is the same or better than baseline, then assign a value of zero.

Longitudinally describing and evaluating disease and treatment-related symptom severity and functional well-being: We will use two graphical approaches to address this objective. First, Locally weighted regression (LOWESS) curves showing symptom trajectories over time for each symptom scales and functional well-being subscales from the EORTC-QLQ C30 will be constructed. Second, we will also construct individual participant profiles for each of the EORTC QLQ C30 symptom scales and functional well-being subscales to describe the individual participants' patterns of change over time. Effect sizes that standardize the difference in symptom improvement or worsening between two preselected time points will be calculated.

Determining meaningful change in disease and treatment related symptoms and functional well-being by using anchors: In order to determine meaningful change in the EORTC QLQ C30 symptom scales and functional well-being subscales, we will use both clinician-rated (Karnofsky) and patient-rated (PGI-Severity, PGI-Change) anchors. We will stratify patients into 3 change groups (improved, no change, declining) between pre-selected time points (e.g. baseline and end of first disease evaluation). The difference in the EORTC QLQ C30 symptom scale scores and functional well-being subscale scores between the pre-selected time points within each of the change groups provide an estimate of meaningful change.

